Analysis of secondary outcome measures as listed in the Aims section such as MG-ADL, MG QOL-15, the MG composite score and TSQM will primarily be conducted only for those who complete the study. We will conduct a two-sided signed-rank test to assess whether these scores changed significantly from baseline (Week 0) to Week 12. In case of missing values for the MG-ADL, MG QOL-15, and the MG composite score in cases where subjects refuse to proceed to Week 12 even though they were responding well on the treatment (as evidenced by the intermediate measurements) or are lost to follow-up, we will impute their Week 12 observation using the last observation carried forward (LOCF) approach. We will also report the proportion of subjects enrolled in the subcutaneous experimental treatment study phase (Week 0 to Week 12) fulfilling our definition of improvement (as mentioned on pg. 24) along with a 95% confidence interval. We will compare between the two phases the percent of subjects meeting the definition of deterioration, worsening, stability and improvement. We will analyze the effect of prednisone dosage (Increase vs Not Increased) on clinical improvement (Yes vs No) using a 2x2 Fisher's exact test in the SCIg phase of the study by comparing dose levels at Week 12 to Week 0 for those patients who complete Week 12 of the study. To do this, we will ask the patients at Week 0, Week 4, Week 8 and Week 12 about their prednisone dosage levels. Those patients who exit the study prematurely due to deterioration before Week 12 will be excluded from this Fisher's test calculations. In the event that the Week 12 prednisone dose observation is missing even when patients have completed Week 12 (QMG or MGADL done), we will use the LOCF approach to impute this missing value as long as at the last available assessment, the patient was deemed to be improving (in terms of QMG or MGADL scores as defined under "Subject deterioration, worsening, rescue medication and improvement"). A two-sided signed-rank test will be also conducted to assess whether IgG levels changed significantly between the intravenous screening phase (Week -10 to Week 0) to the subcutaneous experimental treatment study phase (Week 1 to Week 12). All tests will be conducted at the 5% level of significance. For the secondary outcome measures related to monitoring the safety profile of patients between the two study phases, a similar test will be conducted when the safety parameters measured are continuous variables and a one sample test for the difference in proportions will be conducted when they are measured as treatment-related severity rates. The comparison epochs for safety are also between the intravenous screening phase (Week -10 to Week 0) and the subcutaneous experimental treatment study phase (Week 0 [after first SCIg dose] to Week 12). Adverse events occurring in the two phases (mild, moderate/severe) will be summarized using a McNemar's test.

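### In the prednisone Fisher's test, a missing Week 12 dose is filled only for improving patients and mid-phase increases are ignored, so inclusion depends on the outcome and a few patients can shift the result either way

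*SAP*

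**What the plan says.** Section 3 of the SAP (Analysis of Secondary Outcomes) sets out the analysis: "We will analyze the effect of prednisone dosage (Increase vs Not Increased) on clinical improvement (Yes vs No) using a 2x2 Fisher's exact test". Four rules determine who is in the table and in which row.

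- **Exposure.** Increase or no increase is decided "by comparing dose levels at Week 12 to Week 0 for those patients who complete Week 12 of the study".
- **Dose data.** The same section says "we will ask the patients at Week 0, Week 4, Week 8 and Week 12 about their prednisone dosage levels". Weeks 4 and 8 have no role in the classification; they matter only as a source of carried-forward values.
- **Early exits.** Patients who leave because of deterioration before Week 12 are left out of the test.
- **Missing Week 12 dose in a completer.** LOCF is used "to impute this missing value as long as at the last available assessment, the patient was deemed to be improving", judged on QMG or MGADL. Nothing is said about a completer with a missing dose who was not improving.

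The significance level is 5%. Sidedness is not stated for this test.

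**The concern.** There are two separate weaknesses.

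**Missing doses.** The column variable of the 2x2 table is clinical improvement, and the condition for filling the row variable is also improvement. An improving completer with a missing dose gets an exposure value and is counted. A non-improving completer with a missing dose gets none and, on the natural reading, drops out. Both have completed Week 12 with QMG or MGADL done, so the dose alone is missing and the response is largely known. The section gives no reason to treat that dose differently according to response.

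**Mid-phase increases.** The declared interest is prednisone dosage in the SCIg phase, Week 0 to Week 12. A completer whose dose rose at Week 4 or 8 and is recorded at or below the Week 0 dose at Week 12 is coded Not Increased, although the increase fell inside that phase and was recorded.

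The trial has a single SCIg arm, and this is the only analysis in the SAP that relates a concomitant drug to improvement. Its result should not turn on how a few patients happen to be coded or dropped.

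**Working it through.** The SAP gives no rate of dose change, rate of missing doses or power for this test, so there is no stated figure to reproduce. The only input from the document is the ceiling of 25 patients (section 4, Sample Size Considerations). **Every cell count below is an assumption for illustration.** Tables are written [Increased: improved, not improved] / [Not Increased: improved, not improved]. For cells a, b / c, d the odds ratio is OR = ad/(bc). P-values are two-sided Fisher.

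**Step 1. Mid-phase increases.** Assume 25 completers, 8 of them improved. Classified by any recorded increase, the table is [5, 2] / [3, 15], with OR = (5 × 15)/(2 × 3) = 12.5 and p = 0.017. Now apply the Week 12 versus Week 0 rule when some of the Increased patients are back at or below the Week 0 dose by Week 12.

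| Patients with a temporary rise | Table under the SAP rule | OR | p |
|---|---|---|---|
| none | [5, 2] / [3, 15] | 12.5 | 0.017 |
| 1 improver | [4, 2] / [4, 15] | 7.5 | 0.059 |
| 2 improvers | [3, 2] / [5, 15] | 4.5 | 0.28 |
| 3 improvers | [2, 2] / [6, 15] | 2.5 | 0.57 |
| 1 non-improver | [5, 1] / [3, 16] | 26.7 | 0.006 |
| 2 non-improvers | [5, 0] / [3, 17] | infinite | 0.001 |

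One recoded improver takes the result across 5%. Recoding non-improvers strengthens the association instead.

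**Step 2. The same step from another starting table.** Assume 22 completers and [2, 6] / [10, 4]: OR = (2 × 4)/(6 × 10) = 0.13, p = 0.074. Moving 1 to 4 of the Increased non-improvers gives p = 0.17, 0.35, 0.62 and 1.00. Moving 1 or 2 of the Increased improvers gives p = 0.020 or 0.003. Again both directions occur, and one patient can cross 5%.

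**Step 3. Dropping non-improvers with a missing dose.** Start from [4, 4] / [8, 6]: OR = (4 × 6)/(4 × 8) = 0.75, share improved 12/22 = 55%.

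- Drop 1 to 3 non-improvers, all Increased: OR rises to 1.0 (one dropped) and 3.0 (three dropped).
- Drop 1 to 3 non-improvers, all Not Increased: OR falls to 0.63 and 0.38.
- In both cases the share improved goes to 12/21 = 57% and 12/19 = 63%.

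From the Step 1 table, dropping one Increased non-improver gives [5, 1] / [3, 15], OR = 25, p = 0.007.

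**Step 4. When dropping does not bias the association.** Suppose a fraction m of non-improvers is dropped regardless of dose. Then OR = a·d(1 − m) / [b(1 − m)·c] = ad/(bc), which is unchanged in expectation. Only the share improved moves. With half of all patients improved, it becomes 0.5/[0.5 + 0.5(1 − m)] = 53%, 56% and 59% for m = 10%, 20% and 30%.

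**Step 5. Error in the filled values.** Carry-forward happens only in patients deemed improving, so any error it makes arises only among them. If an improver's dose rose between Weeks 8 and 12 and the Week 12 dose is missing, the patient is coded Not Increased. From [4, 4] / [8, 6], one such patient gives [3, 4] / [9, 6], OR = 0.50; two give OR = 0.30. Conversely, a Week 8 increase carried forward counts as Increased.

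**The case against.** **The end-to-baseline comparison is a legitimate, pre-specified definition.** It matches the Week 0 to Week 12 comparisons used for the other secondary outcomes, and any-increase has its own error because a brief rise counts the same as a sustained one. This stands: the choice between the two is partly preference, so the any-increase version belongs beside the stated one and need not replace it.

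**The problem may rarely arise.** The missing-dose rule applies only when a completer's Week 12 dose alone is absent, and the protocol, which is not shown, may limit prednisone changes. This also stands. The frequency is unknown and could be nil. It does not justify a filling rule that depends on the outcome, since a common rule costs nothing.

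**A stronger reading is tempting but unsupported.** A reader might infer that both rules push improved patients into the Improved, Not Increased cell, so that prednisone looks irrelevant and improvement is credited to SCIg. The SAP does not support this:

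- Steps 1 to 3 show movement both ways.
- The missing-dose rule by itself moves nobody between cells; it decides who stays in the table.
- Observed doses are classified without reference to response, so exposure is not assigned from the outcome.
- Nothing indicates that filled doses would usually be Not Increased.
- The SAP does not say that this test decides what improvement is attributed to, or that patients with a temporary rise are those most likely to have improved because of prednisone.

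**Conclusion.** The point holds in a limited form. Among completers with a missing Week 12 dose, entry into the table is conditional on the outcome being tested. Dropping the non-improvers raises the share improved. The association is biased only if missingness relates to dose or if carrying forward misses a change between Weeks 8 and 12. Separately, the two-time-point rule ignores recorded increases at Weeks 4 and 8 that have gone by Week 12.

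Neither effect has a direction that can be predicted. With at most 25 patients, one or two affected patients can change significance, as the assumed tables show. The actual size cannot be derived from the SAP. The conclusion assumes that non-improving completers without a dose are left out, since no rule is given for them, and that the test is two-sided.

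This is a single secondary, non-randomised comparison. The primary conclusion does not depend on it.

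**What to change.** In section 3 of the SAP:

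1. Replace the conditional LOCF rule with one rule for every Week 12 completer whose Week 12 dose is missing: use the last recorded dose, whatever the patient's QMG or MGADL status. State how many doses were filled.
2. Keep the Week 12 versus Week 0 classification, and report beside it a second 2x2 table in which Increased means any recorded dose above the Week 0 dose at Week 4, 8 or 12.
3. State that the Fisher's test is two-sided, if that is the intention.

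The cost is wording and one more table; the doses are already collected. The drawback is that any-increase treats a brief rise like a sustained one, which is why both versions should be shown.

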**Open Label Study of Subcutaneous Immunoglobulin (SCIg)
in Myasthenia Gravis**

NCT02100969

February 22, 2019

Data Analysis Plan and Statistical Considerations:

1. Analysis of Primary Outcome:

At the end of the 9-week IVIg screening phase, baseline QMG scores of all the patients will be recorded. At the end of SCIg experimental treatment phase (Week 12), the QMG score will be captured and compared to Week 0. If the increase in QMG scores from Week 0 to Week 12 in the experimental treatment phase is found to be no more than 3 points, then they will be considered to be a 'success' in terms of their response. We hypothesize that the positive response rate of these patients is at least 70%. Allowing a margin of 5%, our hypotheses are formally stated below:

Null hypothesis H_0 : Proportion of patients whose QMG scores are increased by more than 3 points at the end of the SCIg treatment phase ≤ 0.65

Alternate hypothesis H_A : Proportion of patients whose QMG scores are increased by no more than 3 points at the end of the SCIg treatment phase > 0.65

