This hypothesis will be tested using a one sided one sample test of proportions with the normal approximation, at the 5% significance level. We will also report a 95% confidence interval for the true proportion of subjects who experience a 'success' as with a sample size of 25 patients, we will have a margin of error of 0.19. In the experimental treatment phase, patients who either experience treatment failure (as previously defined on pg. 22) or clinical deterioration (as defined above on pg. 22) will be withdrawn before Week 12 and we will therefore impute for both non-positive responses at Week 12, a discrete QMG score increase of more than 3 points. For example, if the largest deterioration score observed is 8, then a QMG score ranging between 4 and 8 will be imputed at Week 12. Although we do not expect many missing observations at Week 12 of the SCIg phase, the outcomes recorded at these intermediate time points will allow us the ability to impute data at this endpoint. Specifically, in the case where no outcome is available for a subject at Week 12 due to the subject's perception of a worsened condition, we will impute for this subject a QMG score increase at Week 12 of more than 3 points. In cases where subjects refuse to proceed to Week 12 or are lost to follow-up even though they were responding well on the treatment (as evidenced by the intermediate measurements), we will impute their Week 12 observation using the last observation carried forward (LOCF) approach. We will complement our LOCF approach with sensitivity analyses covering the following alternate approaches: (1) Multiple imputation with 5 replicates per imputation to account for the uncertainty inherent to the imputation (2) Mixed model calculations accounting for the trend in QMG values over time (3) Best case and worst-case scenarios.

2. Additional Exploratory Analysis of Primary Outcomes:

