
4. Sample Size Considerations:

With a sample size of 25 patients, we have at least 70% power to detect a success rate of 85% or higher using the chi-square test compared to an expected success rate of 65% or lower. We anticipate we will be able to assess efficacy, safety and tolerability of SCIg with the current sample size over 12 weeks and compare that these parameters to the 12-week IVIg phase. The selected sample size will enable us to complete study enrollment with the current number of sites.

MG is a rare disease and MG studies have consistently experienced difficulty enrolling subjects due to a multiplicity of poorly understood reasons.³⁴ In the Methotrexate study of MG and similar to other previous MG studies, enrollment has been a challenge. However, we managed to complete enrollment of 50 subjects by adding sites. In the current SCIg study protocol, the eligible

study population is narrowed due to the inclusion criterion requiring MG cases to be on stable IVIg doses. While 85 to 90% of MG patients are seropositive for either the AchR or MuSK autoantibodies, some of these cases are treated in clinical practice with IVIg maintenance. Based on the pre-site selection feasibility survey, 25 subjects is a reasonable and achievable goal with the selected five sites. If enrollment is found to be slower than predicted, we are ready to add more sites to complete this study.

5. Study Populations:

Safety population: All patients enrolled at baseline constitute the safety population. The subjects in this population will be included in the analysis of adverse events, vital signs, clinical laboratory findings, and other safety data. But for the purpose of statistical analyses, the rates of adverse events experienced by these subjects in the SCIg phase will be compared to the rates experienced during the IVIg phase of the study. Adverse events will be tabulated by treatment group, severity, and perceived relationship to study drug. For each adverse event, the treatment groups will be compared regarding the occurrence of at least one event using the Fisher's exact test. The comparisons will be repeated excluding all mild symptoms. Continuous measures such as vital signs and laboratory test results will be analyzed in a manner similar to that for the primary outcome variable.

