Intent to treat population (ITT): Only those patients who receive at least one dose of SCIg are considered to be the primary population which is the same as ITT population. The ITT will be included in the analysis of baseline findings and efficacy results. Only those patients who receive at least one dose of SCIg are considered to be the primary population and the intent-to-treat population.

Unscheduled visits: In the event that there are unscheduled patient visits, we will report the frequency of such visits for the two phases of the study. We will also document the date and reason for such visits and assess if these visits are systematic or random. If occurrence of such visits is due to side effects we will compare the rates of such events across the two phases of the study. Testing at unscheduled visits is done only to check and assess clinical worsening. If no worsening is found, patients will continue to be a part of the study. If a patient experiences a worsening event that does not qualify as clinical deterioration (per pg. 22) and the investigator determines it is safe for that patient to continue, the patient will remain in the study. On the other hand, if a patient experiences a worsening event that qualifies as clinical deterioration the patient will be withdrawn from the study. We will compare the within-person variation to the cross-person variation for the overall data. If the within-person variation is found to be less than the cross-person variation, we will use a LOCF approach to impute the patient's QMG score at the next time point and do a sign rank test on that time point and baseline. On the other hand, if the within-person variation is found to be greater than the cross-person variation, we will impute the observation at the next time point followed by a sign rank test.

SAS 9.4 will be used for all analyses. All data management and statistical analysis will be performed in the Department of Biostatistics at the University of Kansas Medical Center. The Velos Clinical Research Information System (CRIS) will be used at all sites to enter and view data. This will be available to the safety monitors (see below).

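### The SAP gives the IVIg phase three different lengths, and its safety comparison sets 10 weeks of IVIg against 12 weeks of SCIg using occurrence tests with no exposure basis

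*SAP*

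**What the plan says.** The IVIg phase has three lengths in the SAP.

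- Section 1 (primary outcome) times the baseline QMG score thus: "At the end of the 9-week IVIg screening phase".
- Section 3 (secondary outcomes) gives Week -10 to Week 0, once for IgG levels and once for safety: "The comparison epochs for safety are also between the intravenous screening phase (Week -10 to Week 0) and the subcutaneous experimental treatment study phase". The SCIg safety epoch runs from the first dose at Week 0 to Week 12.
- Section 4 (sample size) says that efficacy, safety and tolerability will be assessed over 12 weeks and that the investigators will "compare that these parameters to the 12-week IVIg phase".

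The adverse event analyses are these.

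- Section 3: "Adverse events occurring in the two phases (mild, moderate/severe) will be summarized using a McNemar's test". Safety measures expressed as severity rates get a test for a difference in proportions.
- Section 5, safety population: "For each adverse event, the treatment groups will be compared regarding the occurrence of at least one event using the Fisher's exact test". The same paragraph says that "the rates of adverse events experienced by these subjects in the SCIg phase will be compared to the rates experienced during the IVIg phase".
- Section 5, unscheduled visits, where side effects are the cause: "we will compare the rates of such events across the two phases of the study".

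No denominator in time, common window or exposure adjustment is attached to any of these. Section 1 adds that patients with treatment failure or clinical deterioration during the SCIg phase "will be withdrawn before Week 12".

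**The concern.** All patients receive IVIg and then SCIg, so the between-phase contrast is the comparative safety evidence that this SAP provides. A patient watched for 12 weeks has more opportunity to report an event than the same patient watched for 10. A test on whether at least one event occurred cannot separate that from a product difference. With complete follow-up and the section 3 epochs, the distortion makes SCIg look worse.

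The conflicting lengths add to this. Section 4 reads as though the two phases were equally long, in which case the problem would not arise. Section 3, which actually sets the safety epochs, makes them unequal. An analyst cannot tell from the document whether the imbalance is intended.

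**Working it through.** **Phase lengths.** Section 3: 0 - (-10) = 10 weeks. This matches neither the 9 weeks of section 1 nor the 12 weeks of section 4. The SCIg safety epoch is 12 - 0 = 12 weeks. Under the same weekly hazard, expected event counts on SCIg are 12/10 = 1.20 times those on IVIg; per patient-week the ratio is 1.00.

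**Inputs for the percentages.** From the SAP: windows of 10 and 12 weeks, n = 25, 5% significance level. Assumed, because the SAP gives no event risks: IVIg-phase risk p of 10%, 20% or 50%; the same constant weekly hazard in both phases; everyone followed to Week 12.

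**Formula.** If the 10-week risk is p, the 12-week risk is 1 - (1 - p)^(12/10). The excess is that figure minus p.

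| IVIg risk, 10 weeks | SCIg risk, 12 weeks | Excess (points) | Patients of 25 |
|---|---|---|---|
| 10% | 1 - 0.90^1.2 = 11.9% | 1.9 | 0.5 |
| 20% | 1 - 0.80^1.2 = 23.5% | 3.5 | 0.9 |
| 50% | 1 - 0.50^1.2 = 56.5% | 6.5 | 1.6 |

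The excess is largest where 1.2 × (1 - p)^0.2 = 1, so 1 - p = (1/1.2)^5 = 0.402 and p is about 60%. There it equals 0.402 - 0.402/1.2 = 0.067, or 6.7 points. With equal windows it is zero at every p.

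**Effect on McNemar's test.** Let pI and pS be the risks in the two windows, with the phases independent within patient (assumed). The discordant probabilities are pS(1 - pI) for an event on SCIg only and pI(1 - pS) for an event on IVIg only. At p = 50% these are 0.565 × 0.5 = 0.282 and 0.5 × 0.435 = 0.218, against 0.25 each with equal windows. Summing over all outcomes for 25 patients gives the chance that a two-sided 5% test declares SCIg worse when the hazards are equal. The SAP does not say which version of the test it means, so both are shown.

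| IVIg risk | Exact: equal windows | Exact: 10 v 12 weeks | Asymptotic: equal windows | Asymptotic: 10 v 12 weeks |
|---|---|---|---|---|
| 10% | 0.3% | 0.8% | 2.4% | 3.8% |
| 20% | 1.0% | 2.1% | 2.2% | 4.1% |
| 50% | 1.2% | 3.6% | 2.2% | 5.8% |

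The nominal level in this direction is 2.5%. Positive within-patient correlation would change these figures.

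**Early withdrawal.** Full SCIg follow-up is 25 × 12 = 300 patient-weeks, against 25 × 10 = 250 on IVIg. Under a constant hazard, withdrawals would have to remove 50 SCIg patient-weeks, an average of 2 per patient, before expected event counts were equal. The SAP states neither how many patients will leave nor when.

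**The case against.** The best defence is that section 3 settles the matter: it fixes the safety epoch explicitly, and the 9 weeks in section 1 and 12 weeks in section 4 are narrative that feeds no calculation. This stands in part. The 10-week epoch is the operative one, so the table above uses it alone. A reader might infer a larger distortion by setting 9 weeks against 12, but the SAP does not use a 9-week window for any safety comparison. The defence does not remove the imbalance, since the operative epochs are themselves unequal, and section 4 speaks of a safety comparison on a different footing.

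A second defence is that section 5 already promises rates. It gives no time unit, however, and the tests named are all on proportions or occurrence.

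A third is that early SCIg withdrawal offsets the excess. It may shrink it. A reader might go further and infer that it cancels or reverses it. That needs a withdrawal share and timing that the SAP does not give. The complement of a success rate is not a withdrawal rate, because a patient can reach Week 12 and still not be a success, and section 1 expects few missing Week 12 observations.

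It is also fair to object that the even-handedness of a patient-week rate follows from assuming a constant hazard. That is why the rate is proposed alongside equal windows and not in place of them.

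**Conclusion.** The point holds. The SAP contradicts itself on the length of the IVIg phase, and its operative safety epochs compare 10 weeks with 12 by methods that ignore time at risk.

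Under equal constant hazards and full follow-up, the artefact is 1.9 to 6.5 points against SCIg for the assumed risks, and never more than 6.7. In 25 patients that is one or two people at most. The chance of McNemar's test wrongly showing SCIg worse rises from 0.3–1.2% to 0.8–3.6% (exact) or from 2.2–2.4% to 3.8–5.8% (asymptotic), assuming independent phases. A reader might infer from the exact figures alone that the nominal 2.5% is passed only when events are common. That does not hold for the asymptotic version, and the SAP names neither.

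The effect is modest and falls mainly on the reported percentages. It reaches the secondary safety and unscheduled-visit comparisons only. The primary analysis compares QMG at Week 12 with Week 0 and does not use the IVIg window. The change should be made, but the trial's main conclusion does not depend on it.

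**What to change.** 1. Reconcile the length of the IVIg phase across sections 1, 3 and 4, so that one figure applies throughout.
2. Use windows of equal length in both phases for every between-phase occurrence comparison: McNemar, Fisher and the difference in proportions. Correcting McNemar alone would leave the other two with the same fault.
3. Alongside these, report adverse events and unscheduled visits in each phase per patient-week of actual exposure.

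The cost is a few lines of SAP wording and a small calculation from event, dosing and exit dates.

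There are three drawbacks. Equal windows leave some SCIg weeks out of the paired comparison (12 - 10 = 2 under the section 3 epochs), although those events stay in the full safety tables. Equal windows do not correct for early withdrawal. A patient-week rate averages over time, so if events cluster early in the SCIg phase and patients then leave, the SCIg rate is raised. Reporting both summaries lets the reader see each limitation.

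### The McNemar table for adverse events is undefined: it has no no-event level and no per-patient rule, and read literally it drops patients with an event in only one phase

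*SAP*

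**What the plan says.** Section 3 (Analysis of Secondary Outcomes) compares safety between the IVIg phase (Week -10 to Week 0) and the SCIg phase (from after the first SCIg dose at Week 0 to Week 12) in the same patients. On adverse events it says: "Adverse events occurring in the two phases (mild, moderate/severe) will be summarized using a" McNemar's test. For other safety parameters, "a one sample test for the difference in proportions will be conducted when they are measured as treatment-related severity rates". On significance: "All tests will be conducted at the 5% level of significance".

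Section 5 (Study Populations, Safety population) covers the same ground again. There, "the rates of adverse events experienced by these subjects in the SCIg phase will be compared to the rates experienced during the IVIg phase". Events are tabulated by severity and by relationship to study drug. Event by event, "the treatment groups will be compared regarding the occurrence of at least one event using the Fisher's exact test". Then: "The comparisons will be repeated excluding all mild symptoms".

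Neither section says which yes/no variable enters McNemar's test, whether the unit is the patient or the event, or how to class a patient with no event or with several events of different grades.

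**The concern.** McNemar's test is the right kind of test for this design, because each patient serves as their own control. It works on a table in which every patient is classed once per phase into one of two levels. The only two levels the sentence offers are mild and moderate/severe. If these form the table, a patient without an event in either one of the phases has no cell. The test then asks whether severity changed among patients who had events in both phases, which is a narrower question than whether moderate or severe events became more or less frequent after the switch.

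The people lost in this way include those who had nothing on IVIg and a moderate or severe event on SCIg, and those who moved the other way. Both belong in a between-phase safety comparison. Because the text does not fix the table, the choice could also be made after the data are seen.

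**Working it through.** The SAP gives no figure for this comparison, so there is none to reproduce. Inputs: 25 patients (section 4), a 5% level (section 3), and a two-sided test, which is an assumption because the sidedness of McNemar's test is not stated. All event counts and shares below are assumed.

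**Step 1. How many patients the literal table holds.** Let p be the share of patients with any event, equal in both phases. The number with an event in both phases is 25p² if the phases are independent and 25p if they are fully positively correlated. Under independence, the number with an event in exactly one phase, who have no cell, is 2 × 25 × p(1 − p). Under full correlation it is 0.

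| p | Placed, independence (25p²) | Placed, full correlation (25p) | Event in one phase only, independence |
|---|---|---|---|
| 0.4 | 4 | 10 | 2 × 25 × 0.4 × 0.6 = 12 |
| 0.6 | 9 | 15 | 2 × 25 × 0.6 × 0.4 = 12 |
| 0.8 | 16 | 20 | 2 × 25 × 0.8 × 0.2 = 8 |

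**Step 2. What the test needs.** If all k discordant patients lie in one direction, the exact two-sided P is 2 × 0.5^k. For k = 5 this is 0.0625 and for k = 6 it is 0.031, so at least 6 discordant patients are needed. A table of about 4 patients (p = 0.4, independence) cannot reach that.

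**Step 3. One dataset, several tables.** Assume these worst grades for 25 patients:

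| IVIg \ SCIg | None | Mild | Moderate/severe |
|---|---|---|---|
| None | 6 | 4 | 6 |
| Mild | 1 | 4 | 1 |
| Moderate/severe | 0 | 1 | 2 |

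- Literal table, mild against moderate/severe: 4 + 1 + 1 + 2 = 8 patients placed, discordant 1 against 1, P = 1.00. The 6 patients who went from none to moderate/severe are absent.
- Moderate/severe, yes or no: all 25 placed, discordant 6 + 1 = 7 against 0 + 1 = 1, P = 2 × (1 + 8)/256 = 0.070.
- Mild as worst grade, yes or no: discordant 4 + 1 = 5 against 1 + 1 = 2, P = 0.453. Here a move from mild to moderate/severe counts as losing a mild event, so a yes/no test on mild alone is hard to interpret.
- Any event, yes or no: discordant 4 + 6 = 10 against 1 + 0 = 1, P = 2 × (1 + 11)/2048 = 0.012.

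**Step 4. What section 5 adds.** Repeating the comparison without mild symptoms amounts to moderate/severe, yes or no, and so counts the missing patients. In the same dataset that is 6 + 1 + 2 = 9 of 25 on SCIg against 0 + 1 + 2 = 3 of 25 on IVIg, Fisher P = 0.095. Two limits apply. The test treats 25 patients seen twice as two independent groups. It is also worded event by event, so it may never be run on any moderate or severe event pooled. Suppose 6 patients have a new event on SCIg and none on IVIg: a single event type gives 6 of 25 against 0 of 25, Fisher P = 0.022, but 3 and 3 over two event types give P = 0.235 for each.

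**The case against.** The sentence never says that mild and moderate/severe are the two levels of one table. Where section 3 means a 2x2 table, for prednisone dose, it says so. The parenthesis may list two outcomes, each tested yes or no by phase, and then every patient observed in both phases has a cell. This stands as a possible reading. It does not define the test, because the SAP does not choose between the readings and the results can differ as widely as in Step 3.

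A reader might infer that the main safety signal is left out of the plan. The SAP does not support that. Section 5 compares event rates between phases, tests at least one event against none, repeats this without mild symptoms and tabulates by severity; section 3 also tests treatment-related severity rates. Nor is it true that severe events cannot be seen: the tabulation by severity shows them, and pooling moderate with severe for a test in 25 patients is an ordinary choice.

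A reader might also infer that the test would report no difference whatever SCIg does. That would need the literal reading together with low event rates. Events in the same patient are plausibly positively correlated, and the literal table then holds more than 25p² patients. Finally, no decision rule hangs on this secondary summary.

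**Conclusion.** The point holds for the McNemar comparison itself. Its table is undefined, and its plainest reading drops every patient with an event in only one phase: up to about 12 of 25 at an event share of 0.4 or 0.6 under independence, and fewer as correlation rises. These sizes rest on an assumed event share, equal in both phases, and on 25 patients observed in both.

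The signal is missing from this test, not from the plan. The defect still deserves correction because McNemar's is the only explicitly paired test the SAP names for adverse events, and the Fisher comparison beside it ignores the pairing. That is a fault of method and need not be conservative: the pattern of 6 against 0 gives 0.022 by Fisher and 0.031 by exact McNemar, while the dataset in Step 3 gives 0.095 and 0.070. Overall this is a modest specification error in a secondary safety analysis.

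**What to change.** In section 3, class each safety-population patient observed in both phases by the worst grade in each phase: none, mild, moderate or severe. Run exact McNemar tests on two yes/no outcomes, any adverse event and any moderate or severe adverse event, with no event coded as no. State the sidedness.

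In section 5, replace the unpaired Fisher comparison with these tests, or say how the two relate and which one is reported as the between-phase result. Keep severe events visible in the tabulation by severity that is already planned. A full cross-table of worst grade by phase would be helpful but is optional.

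The cost is a few sentences of SAP wording and minor programming. No new data are needed.
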